a. SF-36 Quality of Life Questionnaire: Total score on this questionnaire will be used to estimate the quality of life in terms of utility. The utility will be estimated based on the tariff validated for Spain (Abellán-Perpignan et al., 2012).

b. Years of life adjusted for quality (QALY). The QALY is the most used measure in economic evaluation. It is a measure composed of years of life and profits (collected from the SF-36) that reflect the quality of life of the population under study. This measure will be used in the cost-utility analysis of the intervention.

c. Body Mass Index (kg / m²). This measure will be used to calculate the cost effectiveness of the neurocognitive training intervention.

d. Cost of health resources that the participants spend (visits to primary care, urgencies, hospital admissions, and medicines consumed).

e. Cost of the time spent by the personnel in charge of the neurocognitive training sessions. A professional with the category of Clinical Psychology for each session of cognitive training with 5 participants, with 1 hour 30 minutes per session for 5 weeks. The cost per hour will be collected according to the salary of the personnel of health centers and institutions of the Andalusian Health Service.

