2. Pre-treatment assessment (session 2; week 1): All participants will complete the following instruments to assess the main and secondary outcomes, and the potential mediators/moderators, exploratory and economic measures: economic and sociodemographic questionnaire; MEDAS; visual analogue scales to evaluate liking, wanting and hunger; food choice task; food liking task; BRIEF-A; IPAQ; DEBQ; FCQ-Tr; PEMS (Coping subscale); RED; DIS; EIEF; WLSE; SOCRATES-00; PSS; mini IPIP; PANAS; UPPS-P; PSRSQ ; FCCS; SF-36, interview about used health resources. The administration order of the tasks will be counterbalanced.
3. Pre-treatment interventions (sessions 3, 4 and 5, week 2):
 - 3.1. Motivational interviewing session: This 90-minute session will be developed in a group format of 5-6 participants.
 - 3.2. Nutrition session: Participants will receive an individualized diet for the following 6 weeks. Videos and brochures about nutrition will be provided, and participants will assist a 60-minute group session with the nutritionist to match and complete relevant information on nutrition and excess weight.
 - 3.3. Physical activity session: Participants will receive physical activity recommendations for the following 6 weeks. Videos and brochures about physical exercise will be provided, and participants will assist a 60-minute group session with the physical exercise instructor to match and complete relevant information on exercise and excess weight.
4. Intervention sessions (sessions 6, 7, 9 and 10; weeks 3, 4, 6 and 7): All sessions will start with Visual Analogue Scales to evaluate hunger, nutrition and physical activity. Each intervention session will be preceded by its pre-treatment evaluation, and followed by its post-treatment evaluation after a week of daily training. The pre and post-treatment evaluation of the impulsive training will be measured by the approach-avoidance bias (with the Tilt-Task app), food choice, the inhibitory control (with the Food Trainer app) and food liking. The pre and post-treatment evaluation of the reflexive training will be

measured by the Now or Later questionnaire for the episodic future thinking training, and the self-registration of nutrition and physical exercise for the implementation of intentions.

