5. Intermediate assessment (session 8; week 5): This assessment will allow the comparison between the interventions for the impulsive and reflexive trainings. It will include: pedometer data; Visual Analogue Scales for liking, wanting and hunger; adherence to diet and physical exercise measured with Visual Analog Scales; Healthy eating with VAS; Exercise habits with VAS; registration of BMI; measure of waist and hip circumference, waist-to-hip ratio and waist-to-height ratio; food choice task; food liking task; PEMS (Coping subscale); DIS; EIEF; WLSE; PANAS; CFCS. The administration order of the tasks will be counterbalanced. After the session, participants will fulfill a self-reported diary with 24-hours food intake.

6. Post-treatment assessment (session 11, week 8): To evaluate the effectiveness of the whole intervention program, the measures of the pre-treatment assessment will be repeated, including: pedometer data; MEDAS, Visual Analogue Scales to evaluate liking, wanting and hunger; adherence to diet and physical exercise measured with Visual Analog Scales; Healthy eating with VAS; Exercise habits with VAS; BMI; measure of waist and hip circumference, waist-to-hip ratio and waist-to-height ratio; food choice task; food liking task; IPAQ; FCQ-Tr; PEMS (Coping subscale); RED; DIS; EIEF; WLSE; PANAS; UPPS-P; CFCS; interview about used health resources. The administration order of the tasks will be counterbalanced. After the session participants will fulfill the self-reported diary with 72-hours food intake.

7. Post-treatment interventions (session 12, week 8): After the post-treatment assessment, participants will have the opportunity to have a second 60-minute group meeting with the nutritionist and another with the physical activity professional, and they will be provided with new 20-minute videos about how to maintain a healthy long-lasting eating and exercise.

After all interventions, participants will be asked to complete a debriefing to register their thoughts and subjective experience about the program.

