8. Follow-up (sessions 13 and 14; week 20 and week 32): Follow-ups at 3 and 6 months after the intervention will include the instruments to obtain the main and secondary outcome measures: pedometer data; Visual Analogue Scales to evaluate liking, wanting and hunger; adherence to diet and physical exercise measured with Visual Analog Scales; Healthy eating with VAS; Exercise habits with VAS; BMI; measure of waist and hip circumference, waist-to-hip ratio and waist-to-height ratio; IPAQ; FCQ-Tr; PEMS (Coping subscale); RED; PSS; mini IPIP; SF-36; interview about used health resources; 72 hours food intake. The administration order of the tasks will be counterbalanced.

Besides, every month after the end of the treatment, participants will be contacted by email and mobile message to explore possible difficulties in following healthy nutritional and exercise habits, and to ask them about their physical activity and healthy goals achievement. The purpose of this contact is, fundamentally, therapeutic adherence.

Participants will be instructed to eat two hours before all evaluation (pre, intermediate and post-treatment, and the two follow-ups) and neurocognitive sessions. Pre, intermediate and post-treatment assessments will be carried out at the same hour.

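### SF-36 is not named at the week 8 assessment; if it is not collected there, the QALY has no utility point between week 1 and week 20

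*Combined protocol and SAP*

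**What the plan says.** Section 2.4, part 5, derives utility from SF-36 through a Spanish tariff and builds the QALY from that utility. Of the QALY it says: "This measure will be used in the cost-utility analysis of the intervention". No other utility instrument is listed.

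The assessment schedule is in section 3:

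- Item 2, pre-treatment, week 1: the list ends "UPPS-P; PSRSQ ; FCCS; SF-36, interview about used health resources".
- Item 6, post-treatment, week 8: the list ends "IPAQ; FCQ-Tr; PEMS (Coping subscale); RED; DIS; EIEF; WLSE; PANAS; UPPS-P; CFCS; interview about used health resources". The health-resource interview is there; SF-36 is not.
- Item 8, follow-ups, weeks 20 and 32: the list includes "RED; PSS; mini IPIP; SF-36; interview about used health resources; 72 hours food intake".

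Item 6 opens with the statement that "the measures of the pre-treatment assessment will be repeated, including: pedometer data; MEDAS", and the other instruments follow. Section 4, under objective 4, says that average cost, BMI and QALY will be estimated per group and compared through incremental ratios. It states neither how QALYs are computed from the utility measurements nor over what period.

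**The concern.** Training runs in weeks 3 to 7, and section 3 presents session 11 in week 8 as the visit that judges the whole programme. If SF-36 is not given there, utility is observed once before training and next at week 20. Anything that happened to utility during treatment, or in the 12 weeks after it, is then inferred from a line between those two points.

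The cost side does not have this gap. Resource use is asked at week 8, and the staff cost of the training sessions is incurred during treatment and counted in full. If the utility benefit is greatest at the end of training, the QALY difference is understated while the incremental cost is not, and the cost per QALY looks worse than it is. The planned bootstrap does not help, because it resamples collected data and cannot restore a utility that was never measured.

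**Working it through.** The plan states no QALY figure, so there is none to reproduce.

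**Inputs from section 3.** Baseline is at week 1, post-treatment at week 8 and the follow-ups at weeks 20 and 32. The schedule is consistent: 8 + 12 = 20 and 8 + 24 = 32. The arms receive the same interventions in week 2 and differ from week 3.

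**Assumptions.** Utility is interpolated linearly between measurements. The between-arm difference is zero at baseline. It is expressed in units of its peak, d, so the percentages do not depend on the size of d. They do depend on its shape over time.

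**Length of the gap.** Without week 8, the first interval is 20 − 1 = 19 weeks of 32 − 1 = 31, or 61%.

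**Formula.** AUC = Σ (t₂ − t₁)(u₁ + u₂)/2 over successive measurements. Share missed = 1 − AUC(weeks 1, 20, 32) / AUC(weeks 1, 8, 20, 32).

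**Full by week 8 and sustained.**
- With week 8: 7 × 0.5 + 12 × 1 + 12 × 1 = 27.5
- Without: 19 × 0.5 + 12 × 1 = 21.5
- Missed: 6 / 27.5 = 21.8%

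**Full by week 8, then linear fade to half at week 20 and zero at week 32.**
- With week 8: 7 × 0.5 + 12 × 0.75 + 12 × 0.25 = 15.5
- Without: 19 × 0.25 + 12 × 0.25 = 7.75
- Missed: 7.75 / 15.5 = 50.0%

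**Difference starting at week 3 instead of week 1.** The rise to week 8 then contributes 5 × 0.5 = 2.5 instead of 3.5, so the true areas are 26.5 and 14.5.
- Sustained: 1 − 21.5 / 26.5 = 18.9% missed
- Fading to zero: 1 − 7.75 / 14.5 = 46.6% missed

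In this case the four-point rule is slightly high, by 27.5 / 26.5 − 1 = 3.8% and 15.5 / 14.5 − 1 = 6.9%. It is still much closer than the three-point rule.

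**Other shapes (start at week 1).**

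| Difference at weeks 8, 20, 32 | With week 8 | Without | Error |
|---|---|---|---|
| 0.75, 1, 1 | 25.125 | 21.5 | 14.4% missed |
| 0.5, 1, 1 | 22.75 | 21.5 | 5.5% missed |
| straight line to week 20, then level | 21.5 | 21.5 | 0% |
| 0, 1, 1 | 18 | 21.5 | 19.4% overstated |
| 1, 0, 0 | 9.5 | 0 | 100% missed |

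**On the QALY scale.** With an assumed peak difference of 0.05, the sustained case is 27.5 × 0.05 / 52 = 0.0264 against 21.5 × 0.05 / 52 = 0.0207. The fading case is 0.0149 against 0.0075. With an assumed 0.03, the sustained case is 0.0159 against 0.0124.

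**On the cost per QALY, with incremental cost unchanged.** The ratio is multiplied by 27.5 / 21.5 = 1.28 (sustained) or 15.5 / 7.75 = 2.00 (fading). With a week 3 start the factors are 26.5 / 21.5 = 1.23 and 14.5 / 7.75 = 1.87.

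**The case against.** The strongest reply is that the plan may already include SF-36 at week 8. SF-36 is a pre-treatment measure, and the opening of item 6 can be read as carrying all such measures forward. The lists are also not complete: item 2 leaves out BMI, the waist and hip measures and the pedometer data, although item 6 treats them as measures being repeated. Figure 1, to which section 3 refers, is not available here. This stands as a real doubt. Against it, the item 6 list is long and specific, and it drops BRIEF-A, DEBQ, SOCRATES-00, PSS, mini IPIP and PSRSQ along with SF-36. Of these, PSS, mini IPIP and SF-36 come back together at follow-up. That looks like a deliberate schedule, though it does not prove one. On either reading, the text does not tell staff clearly whether to give the only utility instrument at week 8.

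A reader might infer that the schedule loses a fifth to a half of any QALY difference. The documents do not support that. They give no utility time course, and the table shows that the error can vanish, reverse or become total. Linear interpolation is also an assumption made here and not the plan's stated method.

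A reader might also infer that effects in general go unmeasured at the end of treatment. That is wrong too: BMI, the effect measure for cost-effectiveness, is recorded at week 8.

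**Conclusion.** The point holds in a conditional form. SF-36 is not named at week 8, and the omission is probable but not certain. If it is not collected there, linear-interpolation QALYs would miss about 19–22% of a between-arm difference that is full by week 8 and sustained, and about 47–50% of one that fades linearly to zero by week 32. The lower end of each range assumes that the difference begins at week 3, the upper end at week 1. For other time courses the error runs from a 19% overstatement through zero to a 100% loss, so neither its size nor its direction can be settled in advance.

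The consequence is confined to the cost-utility part of Objective 4. It does not touch the primary outcome or the cost-effectiveness ratio based on BMI. The change is worth making because it is cheap, and because a week 8 utility that is not collected cannot be recovered later.

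**What to change.** In section 3, item 6, name SF-36 explicitly in the session 11 (week 8) list. This settles the ambiguity under either reading and gives the QALY the post-treatment point that BMI already has.

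In section 4, under objective 4, state that QALYs are computed by area under the curve over weeks 1, 8, 20 and 32, and that the between-group comparison is adjusted for baseline utility. The adjustment is a separate matter from the missing visit, but it belongs in the same sentence: minimization balances age, sex and BMI, not utility, so a chance baseline difference would otherwise carry into the QALY.

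The cost is one questionnaire already in use, at an online session already scheduled. The downside is extra participant burden at a visit with a long battery. A few minutes is a judgement; the documents give no completion time.

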a. *State affect.* Positive and Negative Affect Schedule* (PANAS; Watson et al., 1988): Score in this questionnaire that contains 10 items to evaluate negative affect experienced in the last week, and other 10 items to evaluate positive affect. Two questions about the number of binges and overeating episodes will be included at the end of the questionnaire.

b. *Perceived stress.* Perceived Stress Scale* (PSS; Cohen et al., 1983). Score in this scale with 10 items that evaluates stress feelings experienced during the last month.

c. *Emotional eating.* Coping subscale of the Palatable Eating Motives Scale* (PEMS; Burgess et al., 2014): Score on 4 items that evaluate the intentionality for eating palatable foods to face negative emotions.

d. *Trait food craving.* The Food Craving Questionnaire Trait-reduced* (FCQ-T-r; Meule, et al., 2014): Score on this questionnaire that evaluates the tendency to experience craving.

e. *Reward-related eating.* Reward-Based Eating Scale* (RED; Mason et al., 2017): Score on this scale with 13 items that evaluate worries about foods, losing intake control and absence of satiety.

f. *Nonhomeostatic eating.* Dutch Eating Behavior Questionnaire (DEBQ; Van Strien et al., 1986): Score on this questionnaire that assesses restrictive eating behaviors related to external cues and emotional states.

(3.2) Executive function:

g. Behavior Rating Inventory of Executive Function-Adult Version* (BRIEF-A Spanish version; Roth et al., 2005): Score on this questionnaire that assesses cognitive dysfunction in behavioral and emotional actions in everyday life. Consists of 75 items divided in 9 subscales: inhibition, changes, self-monitoring, initiation, working memory, planning, monitoring task and material organization.

h. Consideration of Future Consequences scale- short food version (CFC; Vilar et al., 2020): Score on 6 items that assess temporal perspective related to health and nutrition, with items oriented to the immediate ("I only act to satisfy immediate concerns, figuring the future will take care of itself") and the future ("I consider how things might be in the future, and try to influence those things with my day-to-day behavior").

(3.3) Motivation:

- i. *Behavioral intention.* Dieting Intentions Scale* (DIS; Cruwys et al., 2013): Score on this 7-item scale about the intentions to follow a diet.

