Based on Cohen's (1992) rule of thumb, clinical significance of change will be reflected by medium within-group effect sizes ($d \geq .5$).

Mediation and/or moderation analysis will be carried out to study the role of variables related to cognition, affect, stress and non-homeostatic food intake, motivation and personality on the program outcome measures.

In addition, possible differences in the program outcomes will be assessed based on sex and weight classification (overweight and obesity -type I and type II).

All the analyses described will be carried out following an intention to treat strategy (ITT) and analysis per protocol (PP). Corrections will always be considered to control for multiple comparisons.

- For objective 4, the average cost and effectiveness (BMI and QALY) for the 3 groups (intervention, sham and treatment as usual) will be estimated. The ratios of incremental cost effectiveness and incremental utility cost will be calculated as the cost and effectiveness difference (BMI and QALY) for the 3 groups. All the analyses will be carried out according to the methodological recommendations for Spain (López-Bastida et al., 2010). The perspective of the health system will be used, including only direct costs. The uncertainty of the results will be carried out through various deterministic sensitivity analysis (AS) and a probabilistic one using nonparametric bootstrapping methods of 1000 iterations (Luce et al., 2001) that will allow to represent the cost-effectiveness plane and the Acceptability curve. The AIP will estimate the variation that the introduction of neurocognitive training would imply for the budget of the public health system, based on the estimated costs of the alternatives compared and the estimated number of patients expected to benefit from the program. Likewise, univariate and multivariate AS will be performed to analyze different budgetary scenarios based on a possible variation in the cost variables and number of beneficiary patients.

**Only in experimental and active control groups (what is not in italics is done by all three groups: experimental, active control, and control) //* Assessment task

Figure 1: Procedure of the program.

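### The itemised week-8 assessment leaves out the PSS although its opening words say the pre-treatment measures are repeated; if the list is followed, perceived stress has no value between week 1 and week 20

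*Combined protocol and SAP*

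**What the plan says.** Section 3 (Procedure) gives the assessment schedule visit by visit.

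- **Week 1, pre-treatment (item 2).** The list includes "BRIEF-A; IPAQ; DEBQ; FCQ-Tr; PEMS (Coping subscale); RED; DIS; EIEF; WLSE; SOCRATES-00; PSS; mini IPIP", so the PSS, BRIEF-A and DEBQ are all taken.
- **Training (item 4).** The sessions are placed as "Intervention sessions (sessions 6, 7, 9 and 10; weeks 3, 4, 6 and 7", each followed by a week of daily practice.
- **Week 5, intermediate (item 5).** The questionnaires end "food choice task; food liking task; PEMS (Coping subscale); DIS; EIEF; WLSE; PANAS; CFCS". The PSS is not among them.
- **Week 8, post-treatment (item 6).** The item opens "the measures of the pre-treatment assessment will be repeated, including: pedometer data; MEDAS" and its list closes "FCQ-Tr; PEMS (Coping subscale); RED; DIS; EIEF; WLSE; PANAS; UPPS-P; CFCS; interview about used health resources". The PSS is not named.
- **Weeks 20 and 32, follow-up (item 8).** The list includes "RED; PSS; mini IPIP; SF-36; interview about used health resources", so the PSS returns.

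Section 2.4, part (3.1), describes the PSS as a 10-item scale that "evaluates stress feelings experienced during the last month". On analysis, section 4 says "Mediation and/or moderation analysis will be carried out to study the role of variables related to cognition, affect, stress and non-homeostatic food intake", and goes on to motivation and personality. It gives no time point for any mediator.

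**The concern.** A variable can be tested as a mediator only if it is measured after training has begun and before the outcome it is meant to explain. Section 4 names three BMI outcomes after baseline: post-treatment, 3 months and 6 months. A reader who follows the itemised lists finds no stress score during training or at its end, so for the first two outcomes nothing is available in the right order.

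What is at stake is the stress part of objective 3.4. A difference in stress first seen at week 20 could be a consequence of weight change since week 8 as easily as a cause of it. A week-8 score that was not collected cannot be recovered later.

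**Working it through.** The plan gives no figure to reproduce here. The check is a comparison of the visit lists in section 3, followed by simple week arithmetic.

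**Where each instrument is named**

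| Instrument | Week 1 | Week 5 | Week 8 (itemised) | Weeks 20 and 32 |
|---|---|---|---|---|
| PSS | yes | no | no | yes |
| BRIEF-A | yes | no | no | no |
| DEBQ | yes | no | no | no |
| Future-consequences scale | yes | yes | yes | no |
| PEMS-Coping | yes | yes | yes | yes |
| FCQ-T-r, RED | yes | no | yes | yes |

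I take the abbreviation FCCS in the week-1 list to be the future-consequences scale.

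**How far the week-8 list departs from week 1.** Counting the three visual analogue scales as one and leaving aside the sociodemographic questionnaire, week 1 names 22 instruments. Seven are not named at week 8: BRIEF-A, DEBQ, SOCRATES-00, PSS, mini-IPIP, PSRSQ and SF-36. So 22 − 7 = 15 are named again. An opening that promises a repeat and a list that drops seven instruments do not agree.

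**Timing of the PSS if the list is complete**

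- Gap between the first and second score: 20 − 1 = 19 weeks.
- Delay from the post-treatment visit to the next score: 20 − 8 = 12 weeks.
- Taking the one-month recall as 4 weeks, which is my assumption, the week-20 score covers weeks 16 to 20 (20 − 4 = 16). Training and home practice run from week 3 to week 8, so none of it is covered.

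**Order of stress and BMI**

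| BMI outcome | Earlier post-baseline PSS if the list is complete | Earlier post-baseline PSS if week 8 is added |
|---|---|---|
| Week 8 | none | none (same visit) |
| Week 20 | none (same visit) | week 8 |
| Week 32 | week 20 | weeks 8 and 20 |

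Outcomes with an earlier stress score therefore rise from 1 of 3 to 2 of 3. A week-8 score would cover about weeks 4 to 8 (8 − 4 = 4), which lies inside the training period. It would still be concurrent with week-8 BMI, so it does not make mediation of that outcome testable in the proper order.

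**Whether another stress measure fills the gap.** The DASS-21 has a stress subscale, but section 2.4, part (4), places it among the screening measures and section 3 uses it only to check exclusions. The PSS is the only perceived-stress scale in the mediating/moderating set.

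**The case against.** The strongest reply is that the PSS is already due at week 8. The item's opening words, read plainly, repeat every pre-treatment measure, and the lists in this section are demonstrably incomplete: the week-1 list does not name BMI, although sections 2.4 and 4 show that baseline BMI is taken. Figure 1, to which section 3 refers for the procedure, is not in the copy reviewed and may settle it. This stands to the extent that the text cannot be said to exclude the PSS at week 8. It does not remove the point, because staff working from the list and staff working from the opening words would give different batteries. The week-5 list carries no promise of a repeat, so the absence there is plain.

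A second reply is that the plan allows prediction and moderation as well as mediation, and a week-1 value is enough for those. That is correct. It leaves untouched only the mediation half of objective 3.4, in which stress is expressly named.

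Stronger readings are tempting, and the documents do not support them:

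- **That the gap equally undermines BRIEF-A and DEBQ.** If the list is complete, both can serve only as baseline moderators or predictors, which the plan already permits. Nowhere does it commit to either as a mediator.
- **That executive function has no questionnaire after baseline.** The future-consequences scale sits under the same heading in section 2.4 and is listed at weeks 5 and 8. Section 4 assesses the executive system through delay discounting and food and exercise behaviours.
- **That non-homeostatic eating is unmeasured after training.** PEMS-Coping, RED and FCQ-T-r are all listed at week 8.

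**Conclusion.** The point holds for the PSS, conditionally. The week-8 item contradicts itself on whether the scale is given. If its list is followed, there is no stress value for 19 weeks, stress cannot be tested as a mediator of week-8 BMI, the week-20 score is concurrent with week-20 BMI, and only week-32 BMI has an earlier post-baseline score. A lagged analysis of the 6-month outcome would remain possible even then, so a reader should not infer that stress mediation is ruled out altogether.

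The conclusion rests on the itemised list being the operative one and on Figure 1 not adding the PSS at week 8; neither can be confirmed from the text. The 4-week recall affects only the statement about which weeks a score covers. The consequence is confined to a secondary objective. The primary BMI comparison does not use the PSS and is unaffected. This is a cheap improvement, not a flaw in the trial's main question.

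**What to change.** In section 3, item 6, reconcile the opening sentence with its list by naming the PSS explicitly at week 8, and check that Figure 1 agrees. In section 4, state that the week-8 PSS is the candidate mediator of week-20 and week-32 BMI.

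The cost is ten questionnaire items at an existing online visit, that is, a few minutes of participant time in an already long battery. If the sponsor always meant the full baseline set to be repeated, the PSS change is one of wording only. I would not ask for BRIEF-A to be added at week 8 on this ground: it has 75 items, and its week-1 value already serves a use that the plan allows. The PSS change has to be made before participants reach week 8.
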